
Exclusion criteria
 
 • Patients with chronic myeloid leukemia, AML of other myeloproliferative disorders Malignant neoplasms with other progression ; • Those who can not control severe infections and other underlying diseases can not tolerate chemotherapy ; • Patients with cardiac insufficiency: ejection fraction (EF)<30%, New York Heart Association (NYHA) standards, Cardiac insufficiency II or above; • Patients with liver and kidney dysfunction: Serum bilirubin (SB)≥2mg/dl, AST is 2.5 times higher than normal upper limit, serum creatinine (SCr) is more than 2.5 mg/dl Serious mental illness uncooperative Refusal to join the study;

Intervention
 
 • Azacytidine 75mg/(m².d) by IV on days 1-7 of every cycle. • Anti-PD-1 mAb 200mg by IV on day 8 of every cycle. • Homoharringtonine(HHT) 2mg/(m².d) by IV on days 1-6 of every cycle Cytarabine 10mg/(m².d) by SC on days 1-7 of every cycle Granulocyte colony-stimulating factor(G-CSF) 300ug/d by SC on days 1-7 of every cycle, until absolute neutrophil count(ANC) > 5X10⁹ / L or white blood cell (WBC) > 20X10⁹ / L.

Total number of patients: 30

Total duration of the study: 3 years

Background

Acute myeloid leukemia (AML) is one of the most common hematological malignancies, a malignant, clonal disease with poor prognosis. The rate of complete remission (CR) was 60%-90% in patients with first induction chemotherapy, 10%~40% became refractory. 70% of AML patients who received the first CR maybe relapsed in the first year after the CR¹. The 5 years total survival (OS) rate of refractory or relapsed AML (RR-AML) was 5%~10%, and the CR rate was not more than 30% in general². There is still no unified treatment regimen for RR-AML, according to Chinese guidelines for diagnosis and treatment (2017 Edition)³ and United States National Integrated Cancer Network (NCCN) 2019 edition AML clinical practice guidelines standard⁴, they still emphasize individualized treatment and salvage chemotherapy. Therefore, how to treat refractory or relapsed acute myeloid leukemia is still an urgent clinical problem.

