Secondary objectives and secondary endpoints:

Number of Participants (Responders) Achieving Overall Response Rate (ORR) After the Eighth Cycle Treatments; time from randomization to death from any cause; The time between the beginning of the group and the occurrence of any event, including death, progression of the disease, chemotherapy regimen, conversion to chemotherapy, addition of other treatment, occurrence of fatal or intolerable side effects, etc; Time between the beginning of randomization and the progression (in any way) of tumorigenesis or (for any reason) death

Research design

Type of study

This is a prospective, single-arm, single-center randomized clinical trial.

Experimental diagram

The overall design of the study is shown in Figure 1.

[figure not shown]

Figure 1. The flow chart of the overall study design

Dosage and administration

Treatment:

Azacytidine 75mg/(m².d) by IV on days 1-7 of every cycle;

PD-1 inhibitor 200mg by IV on day 8 of every cycle;

Homoharringtonine(HHT) 2mg/(m².d) by IV on days 1-6 of every cycle

Cytarabine 10mg/(m².d) by SC on days 1-7 of every cycle

Granulocyte colony-stimulating factor(G-CSF) 300ug/d by SC on days 1-7 of every

cycle , until absolute neutrophil count(ANC) > 5X10⁹ / L or white blood

cell (WBC) > 20X10⁹ / L.

Study process

Screening phase (3 days)

- Inclusion /Exclusion Criteria
- Demographic data: age, sex, nationality, address, spouse's characteristics, contact information.
- Physical examination: height, body weight, blood pressure, body temperature, heart rate, body surface area, respiratory and cardiovascular system examination, nervous system examination, Eastern Cooperative Oncology Group (ECOG) score, etc.
- Laboratory examination:
 - Blood analysis: blood routine test, blood biochemistry
 - BM examination: marrow morphology examination, Flow cytology, etc.

Treatment period (28 days)

- Drugs will be given based on the protocol;
- Blood routine test and blood biochemistry are performed once a day and once a week, respectively;
- T Cellular Subjects and PD-1 are performed before AZA;
- Important vital signs are recorded;
- Adverse events will be recorded and managed according to this protocol.

Termination phase

- Demographic data: age, sex, nationality, address, spouse's characteristics, contact information.
- General information: past history, allergic history, previous disease and status.

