- Physical examination: height, body weight, blood pressure, body temperature, heart rate, body surface area, respiratory and cardiovascular system examination, nervous system examination, ECOG score, etc.
- Laboratory examination:
 - Blood analysis: blood routine test, blood biochemistry,
 - T Cellular Subjects and PD-1 are performed ;
 - Bone marrow examination: marrow morphology examination, flow cytology.

Follow-up phase (6 months)

- Routine blood examination will be repeated once every 1 month;
- The changes of other complications;
- Survival will be long-term recorded until death.

Response evaluation

- Response: According to the 2020 NCCN guidelines.

Safety evaluations

Safety and tolerability are assessed throughout the study.

Safety endpoints

White blood cell count, hemoglobin, liver function, renal function.

Clinical symptoms:

Newly occurred symptoms during the study period: fever, nausea, cough, somnolence, depression, constipation, diarrhea, petechia, edema, pharyngitis, pulmonary edema, atrial fibrillation, tachycardia, mycobacterium avium complex infectious, hyperglycemia, neutropenia, anemia.

Laboratory examination

Blood routine test, blood biochemistry, virological testing, electrocardiogram, etc.

Adverse event**Definition and record of an adverse event**

Adverse events are defined as any harmful medical manifestations occurring in a person who participates in a biomedical research whether this manifestation is related to the research or the product used in the research. An adverse effect may be any unfavourable or unexpected sign (including abnormal laboratory results), any symptom or temporary disorder associated with the use of the product, with or without relation to the product.

The clinically significant abnormality must be reported as an adverse event (AE) in the eCRF, and AE is supposed to record the time of occurrence, the stage of severity, the duration of time, measures and outcomes.

Classification of adverse event severity

Every case report is performed by the grade of severity about drug adverse reactions:

- Mild: usually transient symptoms unaffecting the daily life;

- Moderate: symptoms probably affecting the daily life;
- Severe: symptoms seriously affecting the daily life.

Relevance

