- Definite relevance: The adverse event is clearly related to the investigational agent. For example, an event that follows a reasonable temporal sequence from administration of the study intervention abides by a known or expected response pattern to the suspected intervention, which improves by stoppage and reappears through repeated exposures, but is unable to be reasonably explained by the known characteristics of the subject's clinical state;
- Possible relevance: An adverse event that follows a reasonable temporal sequence from administration of the study intervention abides by a known or expected response pattern to the suspected intervention, which can be easily induced by various other factors;
- Irrelevance: The adverse event is clearly uncorrelated with the research agent or procedure. For example, there exists another plausible cause, and/or a clinically plausible temporal sequence is inconsistent with the onset of the event and the study intervention and/or a causal relationship is considered biologically implausible.

Serious adverse event:

A serious adverse event (SAE) event is defined as the event with one of the following consequences:

- Death;
- Life-threatening condition;
- Hospitalization or extension of hospitalization;
- Temporary or permanent disability;
- Congenital anomaly or malformation;

-
- Important medical events: although the event caused by the drug which may endanger the subjects may not be life-threatening and result in death or require hospitalization, medical or surgical intervention requires to be taken to prevent one of the outcomes based on the appropriate medical judgment.

Definition of an unexpected adverse event:

An unexpected adverse event of the product is defined as the event with the nature, severity or course non-corresponding to the product information mentioned in the summary when it is authorized or in the investigator's brochure when it is not authorized.

Expected adverse events:**➤ Due to myelosuppression**

Neutropenia related infections, fever;

Bleeding: ecchymosis, petechial, haematemesis, hemoptysis, melena, hematuria, etc;

Weary, somnolence, pale, etc (due to anemia);

➤ Due to other non-hematological toxicity

Liver dysfunction;

Renal dysfunction;

➤ Related to the haematological disease

Death

Relapse of any kind

➤ Related to drug allergy

Erythra, edema, pruritus, swelling, etc.

Procedures of all adverse event

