§ Three or more unrelated chromosome abnormalities in the absence of 1 of the WHO-designated recurring translocations or inversions, that is, t(8;21), inv(16) or t(16;16), t(9;11), t(v;11)(v;q23.3), t(6;9), inv(3) or t(3;3); AML with *BCR-ABL1*.

|| Defined by the presence of 1 single monosomy (excluding loss of X or Y) in association with at least 1 additional monosomy or structural chromosome abnormality (excluding core-binding factor AML).

¶ These markers should not be used as an adverse prognostic marker if they co-occur with favorable-risk AML subtypes.

TP53 mutations are significantly associated with AML with complex and monosomal karyotype.

Note: All recommendations are category 2A unless otherwise indicated.

Clinical Trials: NCCN believes that the best management of any patient with cancer is in a clinical trial. Participation in clinical trials is especially encouraged.

RESPONSE CRITERIA DEFINITIONS FOR ACUTE MYELOID LEUKEMIA¹

- **Morphologic leukemia-free state**
 - ▶ Bone marrow <5% blasts in an aspirate with spicules
 - ▶ No blasts with Auer rods or persistence of extramedullary disease
- If there is a question of residual leukemia, a bone marrow aspirate/biopsy should be repeated in one week.
- A bone marrow biopsy should be performed if spicules are absent from the aspirate sample.
- **Complete response (CR)**
 - ▶ **Morphologic CR - patient independent of transfusions**
 - ◊ Absolute neutrophil count >1000/mcL (blasts <5%)
 - ◊ Platelets ≥100,000/mcL (blasts <5%)
 - ◊ No residual evidence of extramedullary disease
 - ▶ **Cytogenetic CR - cytogenetics normal (in those with previously abnormal cytogenetics)**
 - ▶ **Molecular CR - molecular studies negative²**
 - ▶ **CRi - There are some clinical trials that include a variant of CR referred to as CRi. This has been defined as <5% marrow blasts, either ANC <1000/mcL or platelets <100,000/mcL, and transfusion independence but with persistence of cytopenia (usually thrombocytopenia).**
 - ▶ Responses less than CR may still be meaningful depending on the therapy.
- **Partial remission³**
 - ▶ Decrease of at least 50% in the percentage of blasts to 5% to 25% in the bone marrow aspirate and the normalization of blood counts, as noted above.

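### The laboratory safety endpoints name total white cell count but not neutrophils or platelets, so the planned safety results cannot quantify how deep neutrophil and platelet toxicity goes

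*Combined protocol and SAP*

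**What the plan says.** The primary objective covers efficacy and safety together. Under Safety evaluations, the Safety endpoints line reads in full "White blood cell count, hemoglobin, liver function, renal function". Below it, a list of symptoms that are new during the study includes petechia and ends with "mycobacterium avium complex infectious, hyperglycemia, neutropenia, anemia". The laboratory tests are "Blood routine test, blood biochemistry, virological testing, electrocardiogram, etc". The components of the blood routine test are not listed.

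Elsewhere in the combined protocol and SAP:

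- **Regimen.** Dosage and administration lists "Granulocyte colony-stimulating factor(G-CSF) 300ug/d by SC on days 1-7 of every" cycle. The Protocol Summary adds "until absolute neutrophil count(ANC) > 5X10⁹ / L or white blood cell (WBC) > 20X10⁹ / L".
- **Entry.** WBC must be at most 10,000/µL, and hydroxyurea may be used to get there. There is no minimum ANC or platelet count.
- **Monitoring.** For the 28-day treatment period, "Blood routine test and blood biochemistry are performed once a day and once a week, respectively". In follow-up, blood counts are monthly.
- **Adverse events.** Abnormal laboratory results fall within the definition. Abnormalities judged clinically significant go into the eCRF with onset, severity, duration, measures and outcome. Severity is mild, moderate or severe according to effect on daily life.
- **Expected events from myelosuppression.** Infection and fever with neutropenia, symptoms of anaemia, and "Bleeding: ecchymosis, petechial, haematemesis, hemoptysis, melena, hematuria, etc".
- **Response.** Appendix 2 requires an ANC above 1000/mcL for complete response, together with a platelet criterion that begins "Platelets ≥100,000/mcL (blasts <5".

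**The concern.** A laboratory safety endpoint should have a readable direction. WBC does not have one in this setting. It can fall because leukaemic cells clear, which is benefit, or because the marrow is suppressed, which is harm. It can rise with progression or with G-CSF. The protocol anticipates the G-CSF effect, since it sets a WBC threshold for that drug.

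Platelets have no laboratory place in the safety assessment. A fall in platelets shows only as petechia or bleeding, after a clinical consequence has appeared, or as an abnormality that an investigator judges significant enough to report.

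At stake is whether a reader of the trial report can see how far a five-drug regimen lowers neutrophils and platelets. It matters more because the primary endpoint counts CRi as a response, and Appendix 2 defines CRi by a persisting low ANC or platelet count.

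**Working it through.** The plan gives no figure to reproduce. The check sets the safety list beside the rest of the document, with one small calculation.

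**1. Which counts are named, and where**

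| Measure | Safety endpoints line | Symptom list | Expected adverse events | Used elsewhere |
|---|---|---|---|---|
| WBC | yes | no | no | entry limit, G-CSF threshold |
| Haemoglobin / anaemia | yes | anaemia | symptoms of anaemia | – |
| ANC / neutropenia | no | neutropenia, no threshold | infection and fever | G-CSF threshold, Appendix 2 response criteria |
| Platelets / thrombocytopenia | no | petechia only | bleeding only | Appendix 2 response criteria |

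Of the two counts that Appendix 2 uses for marrow recovery, 0 of 2 are in the endpoint line. Thrombocytopenia occurs as a word only in the CRi definition in Appendix 2.

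**2. Does WBC determine ANC?** ANC = WBC × neutrophil fraction. The documents give no differential counts, so the fractions below are assumptions. They illustrate the range and are not trial data.

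- WBC 8,000/mcL (within the entry limit), 2% neutrophils: 8,000 × 0.02 = 160/mcL.
- Same WBC, 12.5% neutrophils: 8,000 × 0.125 = 1,000/mcL, the Appendix 2 threshold.
- Same WBC, 50% neutrophils: 8,000 × 0.50 = 4,000/mcL.
- At the entry limit of 10,000/mcL, ANC is below 1,000/mcL for any neutrophil fraction under 1,000 / 10,000 = 10%.

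One WBC value is therefore compatible with ANC on either side of the threshold. A low ANC in such a patient at entry would come from the disease, not the treatment. The example shows only that WBC does not identify ANC.

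**3. Do other provisions supply the depth?**

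- The symptom list covers new events. With no ANC or platelet minimum at entry, some patients may start cytopenic, and a worsening of that state is not clearly new.
- Adverse-event reporting depends on a judgement of clinical significance that the document does not define.
- The severity scale has no count thresholds. A patient with very low platelets and no symptoms could be graded mild.
- Statistical methods promises an outline for efficacy and safety data, but the only analysis it names is a Kaplan-Meier estimate of 1-year survival. No summary of any count is specified.

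None of these gives the depth of a neutrophil or platelet fall.

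**4. Are the data likely to exist?** The G-CSF threshold needs ANC, and the response criteria need ANC and platelets. It is reasonable to assume that the blood routine test includes a differential and platelets, although the document does not say so.

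**The case against.** The strongest reply is that the endpoint line should not be read alone. It includes haemoglobin, which reflects the marrow. Neutropenia, anaemia and petechia are named directly beneath it, and neutropenia cannot be identified without an ANC. Abnormal laboratory results are adverse events, and the record must include duration. On this view the omission is one of labelling.

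Much of this stands. A reader might infer from the endpoint line that the trial cannot show marrow toxicity at all, or that duration of cytopenia is lost. The documents do not support either inference, because the provisions just listed capture part of the toxicity, and duration is recorded for every event reported. What the reply does not supply is a measure of depth, or any laboratory place for platelets.

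A second reply is that ANC and platelets are confounded too. G-CSF raises ANC, as its ANC threshold shows, and leukaemia lowers both counts. This also stands, and it limits what the replacement can claim. ANC and platelets are still better than WBC, because blasts are not counted in them and a fall below the patient's own starting value can be interpreted. The reply bears hardest on time to recovery: the Appendix 2 thresholds are remission criteria, so days to reach them would largely track response.

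**Conclusion.** The concern holds in a limited form. The named laboratory safety endpoints rely on total WBC and omit ANC and platelets, thrombocytopenia is not named in any safety section, and severity is not graded by counts. As planned, the safety results cannot quantify the depth of neutrophil or platelet toxicity. They can show part of marrow toxicity through haemoglobin, listed events and adverse-event duration.

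The size is qualitative: neither of the protocol's own two recovery counts is a safety endpoint, and no figure in the plan changes. The point should be corrected because safety is part of the primary objective, but it does not affect the response endpoint or the sample size.

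The conclusion that the fix is cheap rests on two assumptions: that the blood routine test includes a differential and platelets, and that the daily schedule given for the 28-day treatment period applies to each cycle. The document states neither.

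**What to change.** In Safety endpoints, replace WBC with ANC and platelet count, and keep WBC as a descriptive variable. Add thrombocytopenia beside neutropenia and anaemia in the symptom list.

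In Statistical methods, specify for each cycle:

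- the ANC and platelet nadir, and the change from the screening value;
- severity categories based on counts, with cut-offs fixed before analysis, alongside the existing daily-life scale.

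Name the screening count as the baseline explicitly, because Statistical methods currently sets baseline at the day of randomization in a single-arm study.

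Time to ANC above 1000/mcL and platelets of at least 100,000/mcL is optional. If it is reported:

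- present it by response status;
- count patients who never recover, die or progress as not recovered;
- identify those already below the threshold at screening;
- limit day-level timing to the treatment period, since follow-up counts are monthly.

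The cost is a little more tabulation, with no new visits or samples if the blood routine test has the assumed components. Reported haematological toxicity may look less favourable. The nadirs will still carry some influence of G-CSF, transfusion and disease, and the report should say so.

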Investigators must immediately take necessarily measures at once to protect subjects' safety, when serious adverse events occur. Furthermore, all adverse

events should be followed up and investigated, and detailed records are supposed to be made and signed.

All serious and non-serious AEs and special situation will be reported from the signature to completion of the subject's last study-related procedure (which may include the follow-up contact for safety). SAEs must be reported using the Serious Adverse Event Form. The sponsor will evaluate any safety information that is spontaneously reported by an investigator beyond the time frame specified in the protocol.

All AEs, regardless of the severity or presumed relationship with the study treatment, must be recorded in the source document and eCRF using medical terminology. Whenever possible, diagnosis should be made when signs and symptoms are caused by the common etiology. Investigators must record their opinions on the relationship between AEs and the study treatment in the eCRF. All measures required for (serious) AEs must be recorded in the source document and reported according to sponsor instructions.

Monitoring committee

A safety committee comprised of 3 persons independent of the trial will be organized and will meet to check the safety related to the study treatment during the study. In terms of the overall mortality of each arm and serious adverse events, review will be performed by the independent safety committee. The committee is responsible for haemovigilance/pharmacovigilance of the study and acts as an additional warning sign against haemovigilance/pharmacovigilance of the study.

Contact

[name] (Email: [contact]), [name] ([contact]),
The First Affiliated Hospital of Soochow University, Suzhou 215006, China.

Statistical methods

Statistical analysis will be done by the sponsor or under the authority of the sponsor. A general description of the statistical methods to be used to analyze the efficacy and safety data is outlined below. Baseline for all analyses will be the day of randomization unless otherwise specified.

Sample size estimation

We used the formula of sample size estimate when comparing the independent rates two groups.

AZA CR/CRi	PD-1+AZA+HAG CR/CRi	Testing effectiveness
18%	38.5 %	80 %

$\alpha=0.05$, bilateral test

Statistical analysis

Kaplan- Meier method was performed to estimate the 1-year survival rate

Procedures

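### The clinical-symptom safety endpoint counts only new symptoms, so worsening of a condition present at entry cannot register on that line

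*Combined protocol and SAP*

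**What the plan says.** The Clinical symptoms item under Safety endpoints covers "Newly occurred symptoms during the study period" and then gives a closed list. The list runs from fever, nausea and cough through petechia and ends with "hyperglycemia, neutropenia, anemia". Worsening is not mentioned, and new is tied to the study period rather than to first dose.

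Three other parts of the protocol bear on the point:

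- The line just before it names laboratory safety endpoints that are not limited to new onset: "White blood cell count, hemoglobin, liver function, renal function".
- The section on the definition and record of an adverse event is broad: "Adverse events are defined as any harmful medical manifestations occurring in a person who participates in a biomedical research". It includes abnormal laboratory results. For each event, "AE is supposed to record the time of occurrence, the stage of severity, the duration of time, measures and outcomes".
- The section on procedures for adverse events sets the collection period: "All serious and non-serious AEs and special situation will be reported from the signature to completion of the" subject's last study-related procedure. It also requires the investigator's opinion on the relationship to study treatment.

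The Statistical methods section announces methods for efficacy and safety data, but the only method that follows is Kaplan-Meier estimation of 1-year survival. It sets baseline at the day of randomization, although the trial is described as single-arm. No rule says how safety events are to be summarised.

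**The concern.** Several of the listed conditions are features of active acute myeloid leukemia as well as possible effects of the regimen. The eligibility criteria set an upper limit for the white cell count but no minimum for hemoglobin or neutrophils, so patients with anemia or neutropenia at entry are not kept out. For such a patient the question of interest is whether the condition became worse on treatment, and a new-onset rule cannot answer it.

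Safety is named in the primary objective next to efficacy. With one arm there is no background rate against which an undercount would show. A reader of the symptom table could take a low incidence of anemia or neutropenia as good tolerability when it partly reflects how many patients already had the condition. The same patients could also yield one anemia figure from the symptom line and another from the adverse event record, with nothing in the plan to say which is the result.

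**Working it through.** The plan states no figure for this endpoint, so there is none to reproduce. The check is on the rule itself.

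**Inputs**
- N = 30, the total number of patients in the Protocol Summary.
- b = share of patients who have the condition at entry. Not in the documents; assumed.
- q = probability of onset or worsening on treatment, taken as the same in patients with and without the condition at entry. Not in the documents; assumed.

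**Step 1. Ceiling on what can be counted.** Only patients without the condition at entry can have it newly occur, so the maximum count is N × (1 − b). For anemia:

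| b (assumed) | Maximum countable | As a share of 30 |
|---|---|---|
| 50% | 30 × 0.5 = 15 | 50% |
| 80% | 30 × 0.2 = 6 | 20% |
| 90% | 30 × 0.1 = 3 | 10% |

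The ceiling applies even if every patient gets worse. The percentages take all 30 patients as denominator; the plan states none. If patients with the condition at entry were removed from the denominator, the percentage would not be capped, but it would rest on 15, 6 or 3 patients.

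**Step 2. Expected loss.** Patients with a new or worse condition number N × q. The new-only rule counts N × (1 − b) × q and misses N × b × q. The share missed is therefore b, whatever q is. At q = 60%, 30 × 0.6 = 18 patients are affected:

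| b (assumed) | Counted | Missed |
|---|---|---|
| 20% | 14.4 | 3.6 |
| 50% | 9.0 | 9.0 |
| 80% | 3.6 | 14.4 |

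Over b = 20% to 80% and q = 30% to 90%, the loss runs from 30 × 0.2 × 0.3 = 1.8 to 30 × 0.8 × 0.9 = 21.6 patients.

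**Step 3. Where worsening can still be seen.** Set against the other sources, the loss is partial:
- Hemoglobin and white cell count are endpoints in their own right, and blood counts are daily during treatment.
- The adverse event definition neither names nor excludes worsening, and severity is recorded.
- Neutrophil count is not among the named laboratory endpoints, and no laboratory endpoint covers fever, cough or petechia. For these the adverse event record is the main remaining source.

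**Step 4. Time before first dose.** Screening is 3 days. Taking follow-up as 182 days and 28 days as one cycle (an assumption), the collection period is 3 + 28 + 182 = 213 days for one cycle and 3 + 224 + 182 = 409 days for eight. Screening is 3/213 = 1.4% or 3/409 = 0.7% of it.

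**The case against.** The strongest reply is that little information is lost. The adverse event definition is wide, onset time and severity are recorded, and hemoglobin, the laboratory measure of the worked example, is itself an endpoint. The baseline prevalences are assumed, so the ceilings only restate the assumption. A fever or cough that resolved and came back could reasonably be called new, so the ceiling is firm only for conditions that persist. All of this stands, and it limits the point to one line of the safety section. It does not repair that line, which is a stated rule and omits worsening.

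A reader might infer more, in three ways that the documents do not support.

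- *Worsening is lost from the trial altogether.* It is not, for the reasons in Step 3 of the working.
- *Off-treatment events are charged to the regimen, because collection runs from signature to the last study procedure.* That is a reporting period, not a rule for what enters a table. Relationship to treatment is recorded, and the relevance scale has a category for unrelated events. Step 4 shows that pre-dose time is very short. The statement "Survival will be long-term recorded until death" concerns survival and does not by itself extend adverse event collection. The lack of a treatment-emergent definition is an omission; any fixed cut-off after last dose would be a convention.
- *Relapse inflates the adverse event figures.* The list of expected events does include "Relapse of any kind", but under the heading for the hematological disease, apart from myelosuppression and other toxicity. Nothing says that it is added to toxicity totals.

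**Conclusion.** The point holds for the clinical-symptom endpoint. As written, it cannot register worsening of a persistent condition present at entry, and its incidences are biased downward. The share of new-or-worse cases missed equals the baseline prevalence, provided that the risk of onset or worsening does not depend on baseline status. The size in this trial is unknown because the documents give no prevalence; the ceilings of 15, 6 and 3 of 30 illustrate assumed values of 50%, 80% and 90%. The response-based primary endpoint and the sample size are unaffected. What suffers is the reading of the safety half of the primary objective, and agreement between the symptom line and the other safety sources.

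**What to change.** In the Clinical symptoms item under Safety endpoints, replace the new-onset wording with: *symptoms that are new, or worse in severity than the last pre-dose record, after first dose*. This also replaces the unclear reference point, since a day of randomization has no evident meaning in a single-arm trial.

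The pre-dose record can come from the screening blood counts for anemia and neutropenia, and from a severity entry at screening for the other listed symptoms. The screening list now has a physical examination and laboratory tests but no explicit symptom severity record. The plan should also state the severity scale used for this comparison and the denominator.

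As a secondary clarification, keep the reporting period as it is and use the recorded onset dates to tabulate events before first dose separately from later ones.

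The cost is one reworded sentence, one short addition on tabulation and one screening entry. The downside is that entry's small burden and some incidences that will look less favourable.

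### The only adverse-event severity scale is defined by symptoms and daily life, so clinically significant laboratory toxicity without symptoms has no usable grade

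*Combined protocol and SAP*

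**What the plan says.** The primary objective covers both efficacy and safety.

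Definition and record of an adverse event brings laboratory findings in: "An adverse effect may be any unfavourable or unexpected sign (including abnormal laboratory results" is how it begins its description of an adverse effect. Entry in the eCRF is mandatory when the abnormality is clinically significant. On content, "AE is supposed to record the time of occurrence, the stage of severity, the duration of time, measures and outcomes".

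Safety endpoints lists "White blood cell count, hemoglobin, liver function, renal function". The list of new clinical symptoms that follows has 17 items and ends with three that are defined by laboratory values: "hyperglycemia, neutropenia, anemia".

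Classification of adverse event severity gives three levels. The lowest is "Mild: usually transient symptoms unaffecting the daily life", the highest is "Severe: symptoms seriously affecting the daily life", and the middle level is worded in the same terms. No other toxicity scale is named or appended.

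**The concern.** The protocol asks for a severity stage on events that its scale cannot stage. The scale asks how far symptoms disturb daily life. A low neutrophil count or a raised liver enzyme may be clinically significant without any symptom, and the scale then offers either the lowest level by default or nothing.

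At stake is what a recorded severity means. Two investigators could grade the same symptom-free value differently, and neither grade would reflect how abnormal it was. A table of mild, moderate and severe events would then say little about laboratory toxicity, which is what all four named safety endpoints measure. The top level also does not separate a severe event from one that is life-threatening or fatal.

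**Working it through.** The plan states no figure on this point, so there is nothing to recompute. The check sets the sections side by side.

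1. *Are laboratory findings adverse events?* Yes, by the definition. Reporting is compulsory for the clinically significant ones, so not every small deviation enters the record.
2. *Must they carry a severity?* Yes. The stage of severity is one of the items the record is to hold, with no exception for laboratory events.
3. *Does the scale have laboratory criteria?* No. Levels with a laboratory threshold: 0 of 3. Levels defined by symptoms and daily life: 3 of 3. Levels for life-threatening or fatal events: 0.
4. *Does another section supply them?* Each candidate serves a different purpose:
   - The multiples of the upper limit of normal in the Protocol Summary are eligibility limits.
   - Appendix 1 (ECOG) grades performance status.
   - The count and blast thresholds in Appendix 2 define response.
   - The list under Serious adverse event defines seriousness, not severity.
5. *Apply the rule.* Take a clinically significant neutropenia with no symptoms. Step 1 makes it a reportable event and step 2 requires a grade. Moderate and severe both need symptoms that affect daily life, so neither fits. Mild also refers to symptoms, so it fits only by default. The result is mild or no defined grade, whatever the count. A symptom-free liver-enzyme rise gives the same result.
6. *Are values available for a better scale?* Yes. Under Treatment period, blood counts are daily and biochemistry is weekly. Both are repeated in the Termination phase.
7. *What depends on the recorded grade?* The only analysis named under Statistical methods is a Kaplan-Meier estimate of one-year survival, which does not use it. Nor does the response endpoint. Serious-event reporting follows its own criteria, including death, life-threatening conditions, hospitalization and important medical events. The safety committee reviews mortality and serious adverse events.

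**The case against.** The strongest reply is that little is lost. Mandatory reporting is limited to clinically significant abnormalities. The four safety endpoints are measured values, and no section says they will be analysed by grade. The raw values are kept, so laboratory grades could be derived later. Serious-event rules work without the scale. For symptomatic events the scale does what it says, and no defect is shown there.

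All of that stands and limits the point. It does not remove it: a clinically significant symptom-free abnormality still reaches the record, still needs a grade, and still has none that fits. Deriving grades afterwards is possible, but it concedes that the recorded severity was not usable.

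Three stronger readings are tempting, and the documents do not support them.

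- *Immune-related toxicity will go unrecorded.* A reader might infer this because a PD-1 inhibitor is given and no immune-related attribution is required in the protocol. But the eCRF and the serious adverse event form are not among the documents and may hold such a field. Procedures of all adverse event also asks for a unifying diagnosis where signs share a cause, and for the investigator's opinion on relatedness. With timing, these would support later adjudication, though not replace the investigator's judgment at the time. Similarly, Relevance says "The adverse event is clearly related to the investigational agent" while Procedures refers to the study treatment; that is a separate wording question.
- *The trial cannot be set against the 11% of level 3-4 immune-related events cited in the Background.* That figure comes from a different regimen, and no section plans the comparison.
- *The small sample shows the size of the flaw.* With 30 patients, an illustrative 3 events has exact 95% limits of 2.1% to 26.5%. That is the precision under any scale.

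**Conclusion.** The point holds for laboratory events. A required field has no usable definition for clinically significant laboratory abnormalities without symptoms, in a trial whose primary objective includes safety and whose named safety endpoints are all laboratory measures.

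Its size is structural: none of the three levels has a laboratory criterion, and there is no life-threatening or fatal level. How many events would be graded misleadingly cannot be estimated from the documents. The consequence is reduced interpretability of the safety data. A reader might infer a failed analysis or missed serious events, but the documents support neither.

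The conclusion assumes that the eCRF does not carry a different severity scale. If it does, the protocol should name it. The immune-related field is a secondary suggestion, because its absence is shown only for the protocol text.

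**What to change.** Replace the three-level scale with NCI CTCAE v5.0 grades 1 to 5, including its laboratory criteria, applied to the blood counts and biochemistry already scheduled.

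Show laboratory grades as shifts from baseline to worst value, because the leukaemia itself lowers counts and a worst grade alone would mix disease with toxicity. State the period each shift covers. For follow-up the protocol says "Routine blood examination will be repeated once every 1 month" and lists no biochemistry, so liver and renal shifts would rest mainly on treatment and termination values.

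Report the number and percentage of patients with any grade 3 or higher adverse event, with an exact (Clopper-Pearson) 95% confidence interval.

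As a secondary change, because the regimen includes a PD-1 inhibitor, add an investigator-assessed immune-related yes/no field to the adverse-event record if the eCRF lacks one.

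The cost is new wording in the protocol and adverse-event form, site training and some coding. No new tests are needed where values are already scheduled, and no change to patient management is proposed.
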